### 8.3.6 SERIOUS ADVERSE EVENT REPORTING

For any AE meeting the specified Serious Adverse Event criteria, the PI or designee will submit an SAE form to NIDCR's centralized safety system via Rho Product Safety. This report may be sent by fax or email. Once submitted, Rho Product Safety will send a confirmation email to the investigator within 1 business day. The investigator should contact Rho Product Safety if this confirmation is not received. This process applies to both initial and follow-up SAE reports.

SAE Reporting Contact Information:

- Product Safety Fax Line (US): [name]
- Product Safety Fax Line (International): [contact]
- Product Safety Email: rho\[contact]

General questions about SAE reporting can be directed to the Rho Product Safety Help Line (available 8:00AM – 5:00PM Eastern Time):

- US: [name]
- International: [contact]

The study clinician will complete a Serious Adverse Event Form and submit via fax or email within the following timelines:

- All deaths and immediately life-threatening events, whether related or unrelated, will be recorded on the Serious Adverse Event Form and submitted to Product Safety within 24 hours of site awareness.
- Serious adverse events other than death and immediately life-threatening events, regardless of relationship, will be reported by fax within 72 hours of site awareness.

All SAEs will be followed until resolution or stabilization.

The principal investigator will report, in summary form, all SAEs to the IRB at the time of continuing review.

---

### 8.3.7 REPORTING EVENTS TO PARTICIPANTS

N/A

---

### 8.3.8 EVENTS OF SPECIAL INTEREST

N/A

---

### 8.3.9 REPORTING OF PREGNANCY

N/A

Based on the NIH Behavioral and Social Intervention Clinical Trial Protocol Template v3.0 - 20180827

## 8.4 UNANTICIPATED PROBLEMS

### 8.4.1 DEFINITION OF UNANTICIPATED PROBLEMS

This protocol uses the definition of Unanticipated Problems as defined by the Office for Human Research Protections (OHRP). OHRP considers unanticipated problems involving risks to participants or others to include, in general, any incident, experience, or outcome that meets all of the following criteria:

- Unexpected in terms of nature, severity, or frequency given (a) the research procedures that are described in the protocol-related documents, such as the Institutional Review Board (IRB)-approved research protocol and informed consent document; and (b) the characteristics of the participant population being studied;
- Related or possibly related to participation in the research (“possibly related” means there is a reasonable possibility that the incident, experience, or outcome may have been caused by the procedures involved in the research); and
- Suggests that the research places participants or others at a greater risk of harm (including physical, psychological, economic, or social harm) than was previously known or recognized.]

### 8.4.2 UNANTICIPATED PROBLEMS REPORTING

Unanticipated problems involving risk to human subjects will be recorded and reported throughout the entire study. The Office for Human Research Protections (OHRP) considers unanticipated problems involving risks to subjects or others to include, in general, any incident, experience, or outcome that meets all of the following criteria:

- unexpected in terms of nature, severity, or frequency given (a) the research procedures that are described in the protocol-related documents, such as the IRB-approved research protocol and informed consent document; and (b) the characteristics of the subject population being studied;
- related or possibly related to participation in the research (“possibly related” means there is a reasonable possibility that the incident, experience, or outcome may have been caused by the procedures involved in the research); and
- suggests that the research places subjects or others at a greater risk of harm (including physical, psychological, economic, or social harm) than was previously known or recognized.

Incidents or events that meet the OHRP criteria for unanticipated problems require the creation and completion of an unanticipated problem report form by the Co-PIs. The report will include the following information when reporting an adverse event, or any other incident, experience, or outcome as an unanticipated problem to the IRB:

- appropriate identifying information for the research protocol, such as the title, investigator’s name, and the IRB project number;
- a detailed description of the adverse event, incident, experience, or outcome;
- an explanation of the basis for determining that the adverse event, incident, experience, or outcome represents an unanticipated problem;

- a description of any changes to the protocol or other corrective actions that have been taken or are proposed in response to the unanticipated problem.

To satisfy the requirement for prompt reporting, unanticipated problems will be reported using the following timeline:

- Unanticipated problems that are serious adverse events will be reported to the IRB and to NIDCR within 24 hours if death or a life-threatening event or within 72 hours for all other serious adverse events.
- Any other unanticipated problem will be reported to the IRB and to NIDCR within 7 days of the investigator becoming aware of the problem.
- All unanticipated problems should be reported to appropriate institutional officials (as required by an institution's written reporting procedures). The IRB will then report to the supporting agency head (or designee), and OHRP. As per Boston University policy: "the HRPP director will report within 21 days of IRB determination of an Unanticipated Problem, serious or continuing noncompliance, or suspension or termination to, as applicable.

All unanticipated problems will be reported to NIDCR's centralized reporting system via Rho Product Safety:

- Product Safety Fax Line (US): [name]
- Product Safety Fax Line (International): [contact]
- Product Safety Email: [rho\\[contact]](mailto:[contact])

General questions about SAE reporting can be directed to the Rho Product Safety Help Line (available 8:00AM – 5:00PM Eastern Time):

- US: [name]
- International: [contact]

---

### 8.4.3 REPORTING UNANTICIPATED PROBLEMS TO PARTICIPANTS

N/A

## 9 STATISTICAL CONSIDERATIONS

### 9.1 STATISTICAL HYPOTHESES

This study is a phase 3 randomized controlled trial to test the efficacy of a video-based smoking cessation induction intervention delivered via VR headset during a dental cleaning (Intervention) vs. a relaxation video control (Control). Both groups will also receive print brochures about EBTs and a 4-week text message program. The Intervention text message program will focus on motivating smoker to

make contact with EBTs while the control text message program will be limited to mediators assessment-only text messages.

#### Primary Endpoints:

Aim 1 Hypothesis 1.1. We hypothesize that, compared to smokers who are randomized to the Control group, smokers who are randomized to the Intervention will be more likely to utilize any EBT (Quitline, clinic-based programs, NCI's text message program, nicotine replacement therapy, other evidence-based medication) during the 7-month post-appointment study period. Alternatively, our null hypothesis is that there will be no difference between the two study groups in EBT contact and utilization during the study period.

Aim 1 Hypothesis 1.2. We hypothesize that, compared to smokers who are randomized to the Control group, smokers who receive the Intervention will have greater tobacco treatment utilization (e.g., more EBTs contacted, more days in the NCI text message program, more days using smoking cessation medication, and more phone/clinic counseling sessions) during the 7-month post-appointment study period. Alternatively, our null hypothesis is that there will be no difference between the two study groups in treatment utilization during the study period.

#### Secondary Endpoints:

We hypothesize that, compared to smokers who receive the Control intervention, smokers who receive the Intervention will:

- a) have more quit attempts during the 7-month study period (Aim 2 Hypothesis 2.1)
- b) have higher motivation to quit at 1-month post-appointment and 3- and 6-months follow-up (Aim 2 Hypothesis 2.2)
- c) have greater biochemically verified abstinence rates at 1-month post-appointment and 3 and 6 months follow-up (Aim 3 Hypothesis 3.1)

Alternatively, our null hypotheses are that there will be no difference between the two study groups on these secondary endpoints.

#### Exploratory Aims:

Aim 4. We will assess mechanisms through which the intervention effects are expected to impact any EBT engagement (self-efficacy, motivation, outcome expectations) and identify subpopulations for whom intervention effects differ (moderators including perceived stress, readiness to quit, gender, and race/ethnicity).

## 9.2 SAMPLE SIZE DETERMINATION

Power calculations focus on the comparison of those randomized to the Intervention vs. Control on our primary outcome of any EBT engagement through a chi-square test at the two-sided  $\alpha = 0.05$  level. We will not adjust p-values for multiple comparisons.

Using the odds ratio as our effect size, we estimate the effect of the Intervention will be  $OR=2.05$  (corresponding to percent with any EBT utilization of 22.7% in the Control vs. 37.6% in the Intervention). Only two published studies tested the efficacy of an intervention on EBT utilization rate, both at 12-months follow-up. Brooks et al reported an EBT utilization rate (i.e., Quitline or clinic-based program) of 29.8% in the intervention group vs. 14.7% in controls ( $OR=2.4$ ). Fu et al reported an EBT utilization rate (counseling or medications) of 44.2% in the intervention and 30.6% in controls ( $OR=1.8$ ). Therefore, we use the average EBT utilization rate in the control groups from these studies (22.7%) as our ‘any EBT utilization’ rate under the null hypothesis in the power analysis. Because neither of the above studies used video or were conducted in a dental setting, we also considered previous studies testing the effectiveness of videos on cessation, which report ORs of 1.9 and 3.0, and previous studies on cessation in dental settings (meta-analysis  $OR=2.38$ ). Based on all the above, we conservatively chose an anticipated effect size of  $OR=2.05$  (corresponding to rates of 22.7% vs. 37.6%). With  $\alpha=0.05$  (two-sided), we need a total sample of  $n=300$  subjects to achieve 0.80 power of detecting this anticipated effect. However, because of potential differences between clinic sites, and assuming an attrition rate of 20% (lost to follow-up or ineligible post-randomization), in consultation with the NIDCR in April 2024 we received authorization to increase the sample size to  $n=455$  subjects ( $n=227$  for intervention and  $n=228$  for control group). Therefore, with  $\alpha=0.05$ , the anticipated effect size of  $OR=2.05$ , and 364 subjects (455 minus 20% lost to follow-up or ineligible post-randomization), we will have 0.87 power to detect the anticipated effect.

For the outcome of the amount of EBT utilization, to our knowledge there are no trials on which to base power. To be conservative, our power analysis was based on an ANCOVA model. Assuming a two-sided  $\alpha=0.05$ , a medium effect size (Cohen’s  $f=0.25$ ), and controlling for confounders, with a total of  $n=364$  participants, we will have 0.92 power to detect group differences.

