Objectives*:	
Primary Objective: To test the efficacy of the Intervention vs. Controls in increasing contact with, and utilization of, EBTs over a 7-month study period.
 
Secondary Objectives: 1) To test the efficacy of the Intervention vs. Controls on quit attempts and on motivation to quit, 2) To test the efficacy of the Intervention vs. Controls on biochemically verified smoking abstinence, and 3) (exploratory) To assess the mechanisms through which the intervention effects occur (mediators) and to identify subpopulations for whom intervention effects differ (moderators).

Endpoints*:	
Primary Endpoint: EBT utilization (any EBT contact, number of EBTs contacted, and duration of EBTs).

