### 3 OBJECTIVES AND ENDPOINTS

OBJECTIVES	ENDPOINTS	JUSTIFICATION FOR ENDPOINTS	PUTATIVE MECHANISMS OF ACTION
Primary			
To test the efficacy of the Intervention vs. Controls in increasing contact with, and utilization of, EBTs over a 7-month study period.	
 
-Any EBT contact over the 7-month study period.
 
-Total number of EBTs contacted – ranging 0 to 4 – over the 7-month study period
 
-EBT utilization index score over the 7-month study period
 
	Because effective cessation programs already exist, innovations are needed to drive smokers to engage with them. 40-80% of smokers are not ready to quit within 30 days, and efforts are needed to reach smokers with motivational interventions in their natural settings. Because we are proactively reaching patients, they may or may not be ready to quit smoking. Therefore, quit rates would be expected to be low if we were focusing on cessation, necessitating a very large sample to be able to compute power. The goal of the study is to test whether a clinic-based intervention that reduces provider burden and has minimal patient burden can drive patients to make contact with EBTs. Our prior research has shown that smokers who are not motivated to quit either lack knowledge about the EBTs, do not know how to access EBTs, and/or have myths about EBTs. The video-based intervention and subsequent 4-week text message program addresses these barriers, and provides motivational strategies to make contact with EBTs.	The VR video intervention including the subsequent 4-week text message program target social cognitive theory constructs (e.g., motivation, self-efficacy, outcome expectations) which are the hypothesized mechanisms that mediate the effect of the intervention on the primary study endpoints.
Secondary			
To test the efficacy of the Intervention vs. Controls in motivating smokers to use a combination of medication and counseling.	-Combination of at least one form of counseling EBTs (state quitline counseling, clinic-based counseling, text messaging) and at least one form of medication (nicotine replacement	Participants may utilize more than one EBT and will be encouraged to do so. Evidence shows that a combination of counseling and medication is more effective than either treatment alone.	

OBJECTIVES	ENDPOINTS	JUSTIFICATION FOR ENDPOINTS	PUTATIVE MECHANISMS OF ACTION
	therapy or tablet medication) over the 7-month study period.		

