### 9.4 STATISTICAL ANALYSES

#### 9.4.1 GENERAL APPROACH

For descriptive statistics, categorical data will be presented through percentages and continuous variables will be presented through means and standard deviations. For statistical tests, a two-tailed  $p$ -value less than 0.05 or a 95% confidence interval not including the null value will be used for statistical significance.

EBT utilization will be analyzed by computing a utilization index score (UIS). The UIS will be created by first computing a proportion of utilization score for each of the EBTs for each participant. For example, a participant who completed 4 of 5 quitline calls has a proportion score of 80. For NRT, the recommended length of treatment is 8 weeks and the proportion completed by each participant will be computed. For the NCI smoke-free text message program, the recommended length of participation is 56 days, and we will compute the proportion of days completed, as well as the proportion of text messages responded to (of those that required a response). For clinic-based programs, the proportion will be calculated as the number of sessions attended divided by maximum number of sessions offered at the corresponding clinic. Because participants may use one or more EBT programs, the overall “utilization index score” will be the sum of the above individual proportion scores of each EBT for each person. These individual scores will be summed to obtain the UIS (continuous variable). The distribution of our UIS will be examined for approximate normality, and transformations to improve normality or categorization of the index score will be considered if appropriate. For primary analyses, we will control for age, gender, and race/ethnicity, along with variables identified through preliminary analyses as significantly differing between study groups.

This study will be registered with Clinical Trials.gov prior to the start of participant enrollment.

A formal Statistical Analysis Plan (SAP) will be completed prior to the completion of the study and the unblinding of the study data.

---

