#### 9.4.3 ANALYSIS OF THE SECONDARY ENDPOINT(S)

Aim 1 Hypothesis 1.2. Dose of EBT utilization. As a secondary outcome, we will examine the total number of EBTs contacted over the 7-month study period (ranging from 0 to 4, for the quitline, any clinic-based program, NCI's text message program, and nicotine replacement or other medication). Participation in the Quitline or NCI's text message program will be based on usage data from the programs. Participation in clinic-based programs or use of smoking cessation medication outside of the quitline will be based on self-report. The number of EBTs utilized will be analyzed through Poisson regression for count data, with the intervention effect described through a rate ratio and 95% confidence interval describing the increased probability of engaging in an additional EBT for those in the Intervention vs. Control. We will control for age, gender, race/ethnicity, and variables identified through preliminary analyses as significantly differing between study groups.

Aim 1 Hypothesis 1.2. Dose of EBT utilization. As a secondary outcome, we will also create a binary indicator of use of a combination of counseling (including quitline, clinic-based programs, and the NCI's text message program) and medications over the 7-month study period. The Intervention will be compared to Control on this outcome through logistic regression, with the intervention effect summarized through an odds ratio and 95% confidence interval. We will control for age, gender, race/ethnicity, and variables identified through preliminary analyses as significantly differing between study groups.

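### The primary endpoint set has one, two or three members depending on the section, with no success rule and no adjustment; if any one win counts, the error is about 7–9%, not 5%

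*Combined protocol and SAP*

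**What the plan says.** The synopsis (section 1.1) gives the primary endpoint as "EBT utilization (any EBT contact, number of EBTs contacted, and duration of EBTs"), which is three measures under one label. Section 3 lists three under Primary: "Any EBT contact over the 7-month study period", "Total number of EBTs contacted" (range 0 to 4) and "EBT utilization index score over the 7-month study period". Section 9.1, under its primary heading, places the number of EBTs contacted inside Hypothesis 1.2.

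The analysis sections differ. Section 9.4.2 covers two outcomes as primary: any EBT by logistic regression and the UIS by linear regression. Section 9.4.3 then says "As a secondary outcome, we will examine the total number of EBTs contacted over the 7-month study period", still under Hypothesis 1.2. Section 9.2 refers to the primary outcome in the singular, as engagement with any EBT, and bases power on comparing it "through a chi-square test at the two-sided" 0.05 level.

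On error control, section 9.4.1 applies one rule to all tests: a two-tailed p-"value less than 0.05 or a 95% confidence interval not including the null value will be used for statistical significance". Section 9.2 adds "We will not adjust p-values for multiple comparisons". No section gives a hierarchy, a testing order, an all-must-succeed rule or any other definition of success on the primary objective. Section 9.4.1 promises a formal SAP before study completion and unblinding.

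**The concern.** Not adjusting is sound when one endpoint decides the trial. It is not sound when several endpoints are called primary, each is tested at the full 0.05, and the plan does not say whether one win is enough. The result that settles the primary objective is then undefined, and so is the error rate attached to that claim. The case that matters is a trial in which any EBT misses significance while the UIS or the count reaches it. As the documents stand, one reader could call that trial positive and another negative, each citing current text.

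**Working it through.** **1. The sections side by side**

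| Section | Any EBT | Number of EBTs | UIS / duration |
|---|---|---|---|
| 1.1 | primary | primary | primary |
| 3 | primary | primary | primary |
| 9.1 | primary (H1.1) | primary (within H1.2) | primary (within H1.2) |
| 9.2 | the primary outcome | not mentioned | powered, no label |
| 9.4.2 | primary | absent | primary |
| 9.4.3 | absent | secondary (H1.2) | absent |

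Duration in the synopsis is taken to be the measure that section 3 calls the UIS. All six sections are current text.

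**2. The plan's own power figure**

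Inputs from section 9.2: 22.7% vs 37.6%, 364 evaluable (182 per arm), two-sided 0.05.
- Mean rate = (0.227 + 0.376)/2 = 0.3015.
- Null SE = √(2 × 0.3015 × 0.6985/182) = 0.0481.
- Alternative SE = √((0.227 × 0.773 + 0.376 × 0.624)/182) = 0.0475.
- Power = Φ((0.149 − 1.960 × 0.0481)/0.0475) = Φ(1.153) = 0.875, against 0.87 stated.

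The stated power therefore spends the whole 0.05 on any EBT.

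**3. Error if a win on any one endpoint counts: outer limits**

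With independent tests, two endpoints give 1 − 0.95² = 9.75% and three give 1 − 0.95³ = 14.3%. The upper bounds are 10% and 15%. These measures overlap heavily, since a participant who uses no EBT scores zero on all three, so independence overstates the error. For equally correlated normal test statistics under the global null:

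| Correlation (assumed) | Two endpoints | Three endpoints |
|---|---|---|
| 0.5 | 9.1% | 12.5% |
| 0.7 | 8.3% | 10.9% |
| 0.8 | 7.8% | 9.8% |
| 0.9 | 7.1% | 8.4% |

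**4. Error with the nesting built in**

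The documents give no correlation and no distribution of multiple use, so both were assumed. Null trials were simulated with 182 per arm, about 20–27% using any EBT, varied shares of users with more than one EBT, and a UIS built as a sum of random proportions over the EBTs used (20,000 trials per scenario). Where correlations were recorded, those between test statistics were about 0.7–0.95. Chance of at least one p < 0.05:
- any EBT or UIS: 7.0–8.4%;
- any of the three, with a robust SE for the count: 7.4–9.4%, mostly 8–9%.

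In about 4% of null trials the UIS or the count is significant while any EBT is not. Those are the trials in which the missing rule decides the conclusion.

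**5. Power for any EBT under each way of closing the gap (364 evaluable)**
- Sole primary, or first in a fixed sequence, at 0.05: 0.875, no added participants.
- Two primaries at 0.025 each: Φ((0.149 − 2.241 × 0.0481)/0.0475) = Φ(0.867) = 0.807. Power of 0.80 needs 360 evaluable, or 360/0.8 = 450 randomized, within the planned 455.
- Three at 0.0167 each: Φ((0.149 − 2.394 × 0.0481)/0.0475) = Φ(0.713) = 0.762. Power of 0.80 needs 396 evaluable, or 396/0.8 = 495 randomized, above 455.

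**The case against.** The best defence is that section 9.2 already names one primary outcome and that Hypotheses 1.1 and 1.2 each carry their own null. If any EBT alone decides the primary objective, its error is 5%; if all endpoints must succeed, it is at most 5%. The sponsor can add that the measures are nested, so the inflation is modest, and that the promised SAP can settle the matter in time.

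Much of this stands. The inflation is conditional, because the documents neither state nor exclude an any-one-wins rule. But section 9.2 describes what the power calculation rests on. It is not a success rule, and sections 1.1, 3, 9.1 and 9.4.2 do not follow it.

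A reader might infer two stronger claims that the documents do not support.
- **An error of 12–16%.** Figures of that size appear when the count is tested with the model-based Poisson SE and 40–60% of users are assumed to use more than one EBT. In that setting the Poisson test alone rejects in roughly 10–16% of null trials, so most of the excess comes from overdispersion in one test, not from multiplicity. It is a separate issue, and no section supports the 40–60% assumption.
- **The status of the count can be chosen once results are known.** Section 9.4.1 commits to an SAP before unblinding. That does not resolve the conflict, but it is a stated safeguard.

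**Conclusion.** The contradiction is real and lies in current text: the primary set has three members in sections 1.1 and 3, two in section 9.4.2 and one in section 9.2, and section 9.4.3 demotes a measure that section 3 calls primary. With 0.05 per test, adjustment declined and no success rule, the error rate of the primary claim is undefined.

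If one win is enough, the rate under the global null is about 7–8% for two endpoints and about 8–9% for three validly tested endpoints, roughly 1.5 to 1.8 times nominal. These figures rest on assumed patterns of EBT use. If any EBT alone decides, the rate is 5% and only the labels are wrong. It should be corrected before unblinding because a correction made afterwards would not be credible.

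**What to change.** Name any EBT utilization over 7 months as the single primary endpoint, as section 9.2 already does. Make the UIS and the number of EBTs key secondary endpoints, each tested at two-sided 0.05 only if the preceding test is significant, with the order written down in advance. The order of those two is the sponsor's choice. Power for any EBT stays at about 0.87 and the sample size does not change.

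If the sponsor wants the UIS to remain primary, keep any EBT and the UIS at 0.025 each and state that a win on either suffices. Power for any EBT is then about 0.81 at 364 evaluable, and the UIS power statement in section 9.2 must be redone at 0.025.

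Under either option, align sections 1.1, 3, 9.1, 9.2, 9.4.2 and 9.4.3. Section 8.1 carries no primary or secondary labels and needs no change. Keep the non-adjustment sentence, but limit it to endpoints outside the confirmatory set. Put the same rule in the SAP. Section 6.3 lists the statistician among those unmasked to treatment condition, so the rule should be dated before anyone sees outcome data by arm.

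Cost: under the fixed sequence the UIS and the count lose standalone confirmatory status if any EBT fails. A protocol amendment is needed, with the funding-agency agreement and IRB approval that the Statement of Compliance requires. The version is dated 12 September 2024 and the study is due to end on 31 July 2025, so there is limited time.

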## 4 STUDY DESIGN

### 4.1 OVERALL DESIGN

This study is a 2-arm, stage III randomized controlled efficacy trial. Three hundred seventy-six patients will be recruited at Boston University GSDM patient treatment center or TU comprehensive care (or Periodontal) clinic, and randomized to the Intervention group or the Control group. To account for participants who become ineligible post-informed consent (e.g., do not complete baseline activities, do not show up to dental visit) and thus are not randomized, we estimate that approximately 700 subjects will be enrolled. Our aim is to test whether the Intervention administered to dental patients during teeth cleaning increases contact with, and utilization of, EBTs. Smokers randomized to the Intervention group will receive: 1) the smoking cessation video intervention via VR headset during their teeth cleaning, 2) brochure about EBTs, and 3) 4-weeks of tailored, interactive, and automated text messages to motivate engagement with EBTs plus periodic text message reminders throughout the study. The Control group will watch a relaxation video through the VR headset during their teeth cleaning, receive a brochure about EBTs, and receive assessment-only text messages. We chose a 'relaxation video' because this topic is at least somewhat connected to the teeth cleaning experience (e.g., to ease dental anxiety and discomfort), rather than watching a video on general health and wellness, for example.

The Primary Objective is to test the efficacy of the Intervention vs. Controls in increasing contact with, and utilization of, EBTs over a 7-month period. Hypothesis 1.1 states: Participants randomized to the Intervention will be more likely to engage (make contact with) EBTs. Hypothesis 1.2 states: Participants randomized to the Intervention will have greater EBT utilization (e.g., more quitline counseling sessions, more days in the text message program).

The Secondary Objectives are: 1) To test the effect of the Intervention vs. Controls on quit attempts and on motivation to quit. Hypothesis 2 states: Participants in the Intervention will make more quit

Based on the NIH Behavioral and Social Intervention Clinical Trial Protocol Template v3.0 - 20180827

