#### 9.4.2 ANALYSIS OF THE PRIMARY ENDPOINT(S)

Aim 1 Hypothesis 1.1. Between group differences in any EBT utilization. The outcome is any EBT utilization over the 7-month study period, including use of the Quitline, clinic-based programs, NCI’s text message program, nicotine replacement therapy, other evidence-based medication (e.g., Bupropion, Varenicline). Quitline use will be based on objective usage data provided by National Jewish Health (the operator of the state's quitline contracted by the Massachusetts Tobacco Cessation and Prevention Program) (e.g., whether contact was made, number of counseling calls, whether patients set a quit date, whether nicotine replacement was requested and delivered to patients), and engagement with NCI’s text message program use (e.g., whether patients opted into the program, response rates, length of time in the program) will be obtained objectively from the program. Data on other EBT utilization (clinic-based counseling; receipt of smoking cessation meds outside of the quitline) will be based on self-report. This binary outcome will be analyzed through a logistic regression model, with the intervention effect described through an odds ratio and 95% confidence interval. We will control for age, gender, race/ethnicity, and variables identified through preliminary analyses as significantly differing between study groups.

Aim 1 Hypothesis 1.2. Dose of EBT utilization. The outcome is our UIS (described in 9.4.1) which summarizes participation in one or more EBTs (the quitline, nicotine replacement or other medications, the NCI SmokefreeTXT program, and clinic based programs). Multiple linear regression will be used to compare the Intervention vs. Control, controlling for age, gender, race/ethnicity, and variables identified through preliminary analyses as significantly differing between study groups. The intervention effect will be described through the slope, representing the difference in mean UIS for those in the Intervention vs. Control group.

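### Section 9.2 gives 0.92 power for the utilization index score, but its stated inputs give 0.997, and the assumed effect f = 0.25 has no stated basis

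*Combined protocol and SAP*

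**What the plan says.** Section 9.2 treats two primary outcomes in turn.

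- **Any EBT use.** The effect is an odds ratio of 2.05, "corresponding to percent with any EBT utilization of 22.7% in the Control vs. 37.6% in the Intervention". The analysable total is 364 ("455 minus 20% lost to follow-up or ineligible post-randomization"), and the stated power is 0.87.
- **Amount of EBT use.** The plan says it knows of no trials on which to base power. It then reports that "our power analysis was based on an ANCOVA model", with two-sided alpha 0.05, a medium effect of f = 0.25, control for confounders and a total of 364, and states that with these "participants, we will have 0.92 power to detect group differences".

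Section 3 lists the UIS as a primary endpoint. Section 9.4.1 builds it as a sum of per-EBT proportion scores. Section 9.4.2 analyses it by multiple linear regression: "The intervention effect will be described through the slope, representing the difference in mean UIS for those in the Intervention vs. Control group". Section 4.1 confirms the number of arms: "This study is a 2-arm, stage III randomized controlled efficacy trial". No mean, SD or dose per user for the UIS appears anywhere.

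**The concern.** The passage gives everything needed to recompute its power, and a medium effect with 182 per arm should give power very close to 1. A printed 0.92 means that either an input or the result is misreported.

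There is also a question of consistency within Section 9.2. The UIS is zero for anyone who uses no EBT, so part of any UIS difference is simply the difference in any-EBT rates, which the preceding paragraph specifies. A reader will want to know whether f = 0.25 is compatible with those rates or needs a further assumption.

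At stake is the only power statement for Hypothesis 1.2. Section 9.4.1 says that a formal SAP is still to be completed, so the figure could be carried into it.

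**Working it through.** **Inputs.** Two arms, 1:1 (Sections 1.1 and 4.1). Total N = 455 × 0.80 = 364, or 182 per arm (Section 9.2). Two-sided alpha 0.05 and f = 0.25 (Section 9.2). Any-EBT rates 0.227 and 0.376 (Section 9.2).

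**1. Check on the neighbouring figure.** Two proportions, 0.227 v 0.376, 182 per arm: power 0.875, against 0.87 stated. That figure reproduces.

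**2. The UIS figure from its stated inputs.** The group effect is one slope, so the F test has numerator df 1 and denominator df 362 minus the number of covariates. Noncentrality is f²N = 0.0625 × 364 = 22.75. Power from the noncentral F is **0.997**, and it stays 0.997 with 0, 3, 5, 10 or 20 covariates. Normal check: √22.75 − 1.96 = 4.77 − 1.96 = 2.81, and Φ(2.81) = 0.9975. The printed 0.92 does not reproduce.

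**3. Settings that come near 0.92.**

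| Setting | Power |
|---|---|
| Total N = 364, alpha 0.025 | 0.994 |
| Total N = 364, alpha 0.01 | 0.985 |
| Total N = 300 | 0.991 |
| 0.25 read as d, 182 per arm | 0.66 |
| Per-arm 182 entered as the total, 1 df | 0.918 |
| Total N = 364, 10 numerator df | 0.925 |
| Total N = 364, 11 numerator df | 0.915 |

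Only the last three are close, and none of them describes a two-arm test on 364 people. Solving at N = 364 with 1 df, power 0.92 needs f = 0.177 (d = 0.35), and power 0.80 needs f = 0.147 (d = 0.29).

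**4. What the any-EBT rates alone imply.** Set UIS = 0 for non-users, and give users in both arms the same dose distribution with mean m and coefficient of variation CV. The documents give no CV, so the values below are assumptions.

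- Mean difference: (0.376 − 0.227)m = 0.149m.
- Variance in an arm with user rate p: m²[p(1 + CV²) − p²].
- d = 0.149 / √(mean of the two bracketed terms), and f = d/2.

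At CV 0 the bracketed terms are 0.227 × 0.773 = 0.1755 and 0.376 × 0.624 = 0.2346. Their mean is 0.2050 and its root 0.4528, so d = 0.149/0.4528 = 0.329 and f = 0.165. Any spread among users raises the variance, so this is the largest f under equal dose, before covariate adjustment.

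| CV among users (assumed) | d | f | Power, N = 364 | Intervention : Control mean dose needed for f = 0.25 |
|---|---|---|---|---|
| 0 | 0.329 | 0.165 | 0.88 | 1.32 |
| 0.5 | 0.281 | 0.141 | 0.76 | 1.56 |
| 0.75 | 0.243 | 0.122 | 0.64 | 1.91 |
| 1.0 | 0.209 | 0.105 | 0.51 | 2.62 |

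Simulated t-tests (20,000 runs each) gave 0.878, 0.765, 0.646 and 0.522.

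**5. What would raise these figures.** Covariates explaining a share R² of UIS variance divide f by √(1 − R²). At CV 0, R² of 5%, 10% and 13.5% gives power 0.895, 0.91 and 0.92; at CV 0.5, R² of 10% gives 0.81. A dose ratio of about 1.04 (CV 0), 1.15 (CV 0.5), 1.28 (CV 0.75) or 1.48 (CV 1.0) gives 0.92 without covariates.

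**The case against.** The strongest reply is that the printed figure errs on the low side. Taken at its stated inputs, the trial has more power for the UIS than it claims. The sample size was set on any EBT use, which Section 9.2 names as the focus of its power calculations, and the plan is open about having no prior trials for the UIS. All of that stands. It limits the severity, but it does not make 0.92 right.

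The second reply concerns equal dose per user, which is not the plan's hypothesis. Hypothesis 1.2 in Section 9.1 expects more EBTs contacted, more days and more sessions in the Intervention arm, and the UIS adds across EBTs, so mean dose per user may well be higher there. The planned model also adjusts for age, gender, race/ethnicity and other variables. This stands too: the range 0.51 to 0.88 is a sensitivity case, not the power of the planned analysis.

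Three stronger readings are tempting, and the documents do not support them:

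- **That 0.92 came from using 10 numerator df.** Entering 182 as the total explains it at least as well, and nothing in the text decides between them.
- **That 0.88 is a ceiling for the UIS analysis.** Prognostic covariates or a modest dose difference would exceed it.
- **That the plan calls its effect size conservative.** In Section 9.2 that word describes the choice of an ANCOVA model; the effect size is called only medium.

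**Conclusion.** The stated 0.92 is wrong for its stated inputs: the value is 0.997, about 8 percentage points higher. This rests only on figures in the protocol and on the 1-df test that a two-arm comparison implies. The origin of 0.92 cannot be determined from the documents.

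Separately, f = 0.25 is unsupported. It exceeds the f of about 0.165 that the any-EBT rates can produce alone, so it implicitly needs a higher dose per user in the Intervention arm, a gain from covariates, or both. The plan quantifies neither. That comparison assumes non-users score zero, equal dose per user and no covariate gain; the power range also depends on CVs that are not in the documents.

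A reader might infer that the trial is underpowered for Hypothesis 1.2. The documents do not show this: the misprint understates power at f = 0.25, and the lower figures hold only under the sensitivity assumptions. The point is a should-fix.

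**What to change.** In the UIS paragraph of Section 9.2:

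1. State that the group test has 1 numerator df.
2. If f = 0.25 is kept, replace 0.92 with 0.997. Otherwise restate the effect size that gives the power claimed (0.92 at 364 corresponds to f of about 0.177, d about 0.35) and say why it was chosen.
3. Add the detectable effect at 0.80 power with 364 participants: f about 0.147, d about 0.29.
4. Add a sensitivity case, labelled as resting on assumed inputs, for the situation where only the any-EBT rates differ: power about 0.88, 0.76, 0.64 and 0.51 at CV 0, 0.5, 0.75 and 1.0 among users. Note that a higher dose per user in the Intervention arm or prognostic covariates would raise these figures.

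The cost is one paragraph, best settled before the formal SAP is written. Neither the sample size nor the planned analysis changes.
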